Specific Aim 1: Compare the effectiveness of an evidence-based HIV risk reduction intervention (MI-HIV) to HIV Education (NIDA Standard) in reducing sex risk behaviors, injection practices, and drug use among a culturally unique sample of disadvantaged, drug-using rural women at high-risk for HIV and HCV. This aim will be accomplished through the random selection of high-risk rural women drug users from rural jails, screening and assessment for high-risk behavior, and random assignment to the HIV-Education or MI-HIV intervention conditions. Follow-up interviews at 3, 6, and 12 months in the community post-release will examine changes in high-risk behavior. It is expected that MI-HIV participants will report significantly greater reductions in risky injection drug use practices, other drug use, and sex risk behaviors than women who participate in the HIV-Education condition.

Specific Aim 2: Examine MI-HIV Intervention engagement as a predictor of community health and behavioral health service utilization (including drug treatment and mental health) at follow-up among disadvantaged, drug-using rural women at high risk for HIV and HCV. This aim will focus on community service utilization during the follow-up period by the intervention and education comparison group, and how health and behavioral health service utilization relates to patterns of HIV/HCV risk behavior. It is expected that MI-HIV participants will utilize more services due to increased motivation for treatment and treatment planning following the brief intervention.

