7. **Research Procedures:** The research procedures for this study can be described as screening, baseline interview, intervention, and follow-up.

Screening: Following random selection, the purpose of the screening session is to initially identify rural women engaging in moderate to high-risk drug use. The screening session (estimated 20 minutes) will be conducted between a trained study interviewer and the potential participants either in a face-to-face format or in a group setting, depending on the jail accommodations. The session will include informed consent and an emphasis on the voluntary nature of study participation (see *Human Subjects Protections* section). Following consent, participants will be administered the NIDA-modified ASSIST to screen for moderate to high-risk drug use (NIDA, 2009). If the screener is administered in a group format, ASSIST questions will be read aloud to participants and responses will be recorded confidentially on paper copies of the screener. The ASSIST was developed and validated by the WHO for both men and women (Humeniuk & Ali, 2006) to detect substance abuse risk in health care settings. The NIDA-modified ASSIST was selected for use in this study because it can be administered by an interviewer, and scores can be used to interpret participant risk levels that map to indicators for brief intervention (defined in this study as either the HIV-Education or MI-HIV conditions). An ASSIST score of 4+ (identified as being at moderate risk with potential benefit from receiving a brief intervention) will be considered the cutoff score for entry into the study as the goal is to include as many rural women as possible rather than limiting enrollment to only those who are likely to meet criteria for abuse or dependence.

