9. **Potential Risks:** The procedures to be used by this study will involve conventional clinical and social science research methods that are routine in studies of this type. The potential psychological risks will be discussed with participants during recruitment contacts to assist them in making an informed decision as to whether they wish to participate in a study protocol. These potential psychological risks are primarily related to being asked questions in the interview that they do not feel comfortable asking. There is also a risk that for participants assigned to the MI-HIV condition, there may be a breach of confidentiality of their study files or counseling information. Every effort will be taken to ensure that this does not happen. Therapist records for client sessions will be completed and stored in the research office at UK. No files – hard copy or electronic – will be stored in the jail. For participants who are not randomized in to the MI-HIV condition that they may have to wait to get in to treatment services in the community. These risks will be discussed with each potential study participant during the informed consent process.
- Screening for substance use with a criminal justice involved sample can be biased by a participant's willingness to self-report behavior (Maggia, et al., 2004; Reinert & Allen, 2007), particularly when there may be perceived consequences. Therefore, confidentiality issues will be stressed during informed consent which will include the description of a federal Certificate of Confidentiality which provides an additional layer of human subject protection. Participants will also be assured that their screening results, HIV test results, study participation, and study data will not be made available to any representative of the jail or criminal justice system. Jail officials and administrators will not be informed of participants who participate in the screening, eligibility data, or refusals in order to protect participant confidentiality.

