13. **Research Materials, Records, and Privacy:** Self-reported behavioral data will be collected at the baseline and at 3, 6, and 12 months post-release from jail for follow-up interviews, along with HIV/HCV Orasure tests. The study interviewer will attend an intensive week-long training that covers topics including human subjects protection and issues that could arise during jail-based data collection. For example, training will be conducted on the importance of ensuring that all materials brought in to the jail are also taken out of the jail by the interviewers (e.g., pens, study materials, etc). A variety of behavioral data including demographic characteristics, past drug use, injection drug use, health and mental health problems, and service utilization will be collected through self-reports using Computer Assisted Personal Interviewing. administration with a portable computer (DELL notebook). During the CAPI portion of the interview, the trained interviewer will read the instructions, questions, and response categories from a laptop and directly enter the participant's response. The CAPI formatting will be programmed using Questionnaire Development System (QDS™) from Nova Research (<http://www.novaresearch.com>). Data with the participant ID and all other identifying information (consent form, locator sheet, payment forms) will be stored separately. Consent forms, locator sheets, and payment forms will be managed on site. Security of the data will be maintained through regular computer server backups and CD Rom back-ups secured in fire-safe locked boxes. In addition, data will be collected in brief intervention sessions with the study therapist on engagement, participation, number of services attended, session content, and needed service referrals. Measures of adherence to the MI-HIV intervention will also be collected. No clinical data (including missed sessions) will be provided to jail officials or any other criminal justice official. Participation in this study will not be considered in probation or parole decisions.
14. **Confidentiality:** Every effort will be made in the protection of human participants and issues relating to participant confidentiality. Because this study will involve individuals who are incarcerated, this study's human participants' protocol will comply fully with the special protections pertaining to behavioral research involving prisoners as participants.

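### Aim 1 outcomes are self-reports read out and keyed by an interviewer, with no stated masking to arm, so socially desirable reporting could differ by arm and favor MI-HIV

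*Protocol*

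**What the plan says.** Specific Aim 1 states its expectation in terms of reporting: "MI-HIV participants will report significantly greater reductions in risky injection drug use practices, other drug use, and sex risk behaviors" than women in HIV Education. The source is named in the same aim: "Follow-up interviews at 3, 6, and 12 months in the community post-release will examine changes in high-risk behavior".

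Section 13 (Research Materials, Records, and Privacy) confirms that "Self-reported behavioral data will be collected at the baseline and at 3, 6, and 12 months post-release from jail for follow-up interviews". It lists domains including "past drug use, injection drug use, health and mental health problems, and service utilization will be collected through self-reports using Computer Assisted Personal Interviewing". In that mode "the trained interviewer will read the instructions, questions, and response categories from a laptop and directly enter" the woman's response. The list is open-ended and does not name sex risk, but no other mode is described for it.

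Interviewer preparation is an "intensive week-long training that covers topics including human subjects protection and issues that could arise during jail-based data collection". Masking to arm is not mentioned there or anywhere else in the protocol.

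Section 7 (Research Procedures) places randomization after the baseline interview. It gives both arms the NIDA Standard education and the HIV/HCV test counseling. MI-HIV adds at least four and at most 12 sessions with a study interventionist, including phone sessions at 30 and 60 days after release. The HIV/HCV tests are voluntary (section 20) and do not measure drug use, injection practice or sex risk.

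**The concern.** Women cannot be masked, because MI-HIV consists of extra sessions. Those sessions identify a woman's risky sex and drug use, explore how ready she is to act on it, and then discuss changing it. The last scheduled call, at 60 days, falls about a month before the 3-month interview. A woman who has talked through change with study staff is then asked aloud by study staff whether she changed.

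If that leads more MI-HIV than HIV-Education women to deny a behavior that continues, the reported difference moves in the direction of the hypothesis even if behavior is the same in both arms. This would be a shift in the estimate, which a larger sample does not cure. With no objective measure of the behaviors, the analysis has nothing to correct it against. An interviewer who knew the arm could add to it through tone, probing or coding.

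Because randomization follows the baseline interview, only the follow-up interviews are exposed. Who collects the outcomes, what they know and who enters the answers are protocol decisions, so this is not a matter left to an analysis plan.

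**Working it through.** **Plan's own figures.** Section 3 gives 175 + 175 = 350, which agrees. The protocol gives no prevalence at follow-up, effect size, significance level or figure for reporting bias. What follows illustrates sensitivity and does not estimate the bias.

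**Inputs**

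- n = 175 per arm (section 3), with complete follow-up assumed.
- True prevalence p, equal in both arms: one-third, borrowed from the share section 4 expects to have ever injected; 50% is an added assumption.
- Extra denial u: the fraction of MI-HIV women with the behavior who deny it, over and above any denial in HIV Education. Assumed 5%, 10% and 15%.
- Two-sided 5% level (assumed).

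**Formulas**

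- Reported prevalence in MI-HIV: q = p(1 − u).
- Spurious difference: d = p − q = pu.
- Standard error: SE = √{[p(1 − p) + q(1 − q)]/n}.
- Type I error: Φ(−1.96 + d/SE) + Φ(−1.96 − d/SE).

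**Worked line, p = 0.50, u = 0.10**

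- q = 0.45 and d = 0.05.
- SE = √[(0.2500 + 0.2475)/175] = 0.0533, so d/SE = 0.938.
- Type I error = Φ(−1.022) + Φ(−2.898) = 0.153 + 0.002 = 0.155.

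**Worked line, p = 1/3, u = 0.10**

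- q = 0.30 and d = 0.0333.
- SE = √[(0.2222 + 0.2100)/175] = 0.0497, so d/SE = 0.671.
- Type I error = Φ(−1.289) + Φ(−2.631) = 0.099 + 0.004 = 0.103.

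**Results**

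| Prevalence | Extra denial | Spurious difference (points) | Two-sided type I error |
|---|---|---|---|
| 1/3 | 5% | 1.7 | 6.3% |
| 1/3 | 10% | 3.3 | 10.3% |
| 1/3 | 15% | 5.0 | 17.4% |
| 50% | 5% | 2.5 | 7.5% |
| 50% | 10% | 5.0 | 15.5% |
| 50% | 15% | 7.5 | 29.2% |

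A pooled-variance test gives nearly the same values (10.3% at one-third and 15.5% at 50%, both for 10% denial). If only 140 per arm were followed (an assumption), 10% denial gives 9.2% and 13.4%. Losses dilute the inflation slightly, but the spurious difference itself does not change.

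**The case against.** Several stronger readings are tempting, and the protocol does not support them.

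- **Interviewers know the arm.** A reader might infer this, but the protocol never says so. It describes the interviewer and the interventionist as separate roles, and section 14 has instruments identified by number only. What can be said is that no provision for masking or for keeping the roles apart is stated.
- **Control women have no comparable contact.** They receive manualized education on the same risk behaviors, with condom use rehearsed, and test counseling as the other arm does. Both arms hear which answers are desirable. Any differential can come only from the added MI sessions.
- **The protocol concedes that its outcomes are biased.** Section 9 says "Screening for substance use with a criminal justice involved sample can be biased" by willingness to disclose. That sentence concerns screening and perceived consequences, and the answer given is confidentiality. It does not address outcome interviews or bias that differs by arm.
- **The protocol already prefers private self-entry.** In group screening, "responses will be recorded confidentially on paper copies of the screener", but the text does not say that the woman writes them herself. Privacy there has its own reason, since other inmates are present.
- **The direction is established.** Rapport with study staff could also increase disclosure. A bias toward MI-HIV is plausible, not shown.
- **Analysis is powerless.** Sensitivity analyses can bound the effect of assumed differential reporting. They cannot correct it without an outside measure.

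It is also fair to say that interviewer-administered computer interviewing is an accepted mode, and that choosing self-entry is partly a matter of preference. What stands is the combination: self-report only, unmaskable participants, extra behavior-focused contact in one arm, and no stated safeguard at the outcome interview.

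**Conclusion.** The point holds in a limited form. Aim 1 rests on self-reports given to an interviewer, with sex risk presumably collected in the same mode. No masking or separation of roles is stated for follow-up, and no objective measure of the behaviors is planned. Reporting could therefore differ by arm, plausibly in favor of MI-HIV.

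The size is unknown. Even modest extra denial would matter: on the assumptions above, 10% takes a nominal 5% error rate to about 10% at one-third prevalence and 15.5% at 50%. The denial rates, the 50% prevalence, the use of an ever-injected figure as a prevalence at follow-up and full retention are all assumptions.

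This does not show that the trial's result would be false. It shows that a positive result could not readily be told apart from a difference in reporting. The change should be made because it is cheap and cannot be made after the data are collected.

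**What to change.** 1. In section 13, state that the interventionist conducts no outcome interviews, that follow-up interviewers are not given arm assignment, and that they ask each woman not to disclose it.
2. For the injection, drug-use and sex-risk items, at baseline and every follow-up and in both arms, let the woman enter her own answers out of the interviewer's view. The interviewer reads the questions from a printed script, since the present mode has the interviewer reading from the laptop and one screen cannot serve both purposes. State explicitly that sex-risk items are included.

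**Cost.** The interview screens need some reprogramming, and a printed script has to be kept in step with the skip patterns. Interviews will be slightly longer and a few more items may be skipped. The interviewer and interventionist are already described as separate roles, so no new staff are needed. Having the questions read aloud limits literacy problems.

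**Limit.** Masking the interviewer and private entry reduce the bias but do not remove it, because the women know their arm. The report of results should say so.
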